### 5.3.3 Access to IMP after the End of Study Participation

Subjects will not be provided with IMP by CSLB after completion or discontinuation from the study.

## 6 Allocation to Treatment

### 6.1 Subject Assignment

After providing written informed consent, the subject will be issued with a study-level unique subject identification number via an IRT system. The subject identification number will be used to identify the subject for the duration of the study. Subject identification numbers will not be reassigned. If a subject is rescreened, the original subject identification number will be used.

## 6.2 Randomization Procedures

Eligible subjects will be randomized to 1 of the 2 double-blind treatment sequences by means of IRT. The IRT will assign the IMP to each subject and the correct dose volume based on the subject's body weight. Randomization will be done centrally and CSLB will supply the investigator with a user guide for the IRT.

Randomization will be stratified by region (Japan vs. non-Japan) and by MMT-8 assessment ( $\leq 142$  points vs.  $> 142$  points) to ensure even distribution of subjects to treatment sequences within stratum. For subjects with MMT-8 score at Baseline of  $\leq 142$  points and a muscle group not able to be assessed because of a non-DM related injury or an amputation, the Evaluating Physician will need to determine the appropriate stratification according to DM with muscle weakness (classic DM,  $\leq 142$  points) or DM with little or no muscle weakness (hypo/amyopathic DM,  $> 142$  points) and assign appropriate stratum for this subject.

The randomization list will be generated by the IRT external service provider according to the approved randomization specifications. The IRT external service provider will keep the randomization code on file.

## 6.3 Blinding Procedures

### 6.3.1 Blinding Method

Throughout the study, the IMP will be dispensed in 50-mL vials in blinded packaging that ensures IgPro20 will not be distinguishable from the placebo.

Adequate procedures are in place to ensure the integrity of the blinded data within CSLB. Study data will be provided to the IDMC as unblinded data, as requested. These procedures are outlined in the IDMC Charter and a separate Study Blinding/Unblinding Procedures document.

Serum IgG levels will not be disclosed to the investigative site or any blinded study personnel before unblinding the study.

### 6.3.2 Breaking the Blind for an Emergency

The randomization code for individual subjects may be unblinded to a site during the study in emergency situations for reasons of subject safety, if knowing treatment assignment will change subject management. In case of an emergency situation for the reason of subject safety, the investigator should use the IRT to identify the treatment allocation for a subject. Whenever possible, the investigator should consult with CSLB before unblinding the

---

randomization code. The reason for unblinding the randomization code must be fully recorded in the subject's source documents, and the investigator must follow the defined procedures provided in the study reference manuals. The subject's treatment allocation should not be recorded in the subject's source document.

### **6.3.3 Planned Unblinding Procedures**

CSLB will authorize that the study be unblinded for analysis after all subjects have completed all assessments for Study Period 1 and the data has been cleaned for primary data analysis:

- CSLB employees will be blinded to treatment allocation until all subjects have completed all assessments for Study Period 1 and the data has been cleaned for primary data analysis. Site monitors will remain blinded to treatment allocation until all subjects have completed all assessments for Study Period 2.
- Subjects and caregivers, as well as site personnel involved in the conduct of the study, will be blinded to treatment allocation until all subjects have completed all assessments for Study Period 2.

### **6.3.4 Ad hoc Safety Unblinding**

CSLB's Global Clinical Safety and Pharmacovigilance personnel may, on an ad hoc basis, unblind the randomization code directly in the IRT at any time during the study because of a safety concern. The purpose of the unblinded data review is to determine if there is a risk to subject safety that would require further action either for the individual management of a study subject or for the ongoing conduct of the study. The need to unblind a subject or group of subjects may not necessarily arise because of an SAE. The need to unblind on an ad hoc basis will be determined by CSLB's Global Clinical Safety and Pharmacovigilance.

## **7 Contraindications, Permitted Therapies and Prohibited Therapies**

### **7.1 Contraindications and Precautions to Further Dosing**

IgPro20 is contraindicated in IgA-deficient patients with antibodies against IgA and with a history of severe systemic hypersensitivity or anaphylactic reactions/anaphylaxis to the active substance of IgPro20 or to any of its excipients (L-proline stabilizer and polysorbate 80).

IgPro20 must not be administered if hyperprolinemia type I or II condition exists [IgPro20 IB].

## 7.2 Permitted Therapies

The following therapies are PERMITTED during the study (note: this list is not intended to be all inclusive) provided a stable dose/regimen has been achieved according to the designated time period (in parentheses) before Baseline:

- Prednisolone equivalent ( $\leq 20$  mg/day, except for oral rescue corticosteroid treatment [Table 6]), topical corticosteroids (low to medium potency), inhaled corticosteroids, topical immunosuppressants, physiotherapy (1 month). Taper of concomitant oral corticosteroid dose is required starting at Week 17 if the subject has demonstrated clinically relevant improvement (see [Section 5.3.2](#)). Monitoring for corticosteroid side effects should continue (see [Section 8.1.2.1](#)).

**Table 6** **Corticosteroid Dose Equivalency**

Corticosteroid	Equivalent Dose	Corticosteroid	Equivalent Dose
Prednisolone	20 mg	Betamethasone	2.4 mg
Prednisone	20 mg	Dexamethasone	3.0 mg
Methylprednisolone	16 mg	Hydrocortisone	80 mg
Triamcinolone	16 mg	Cortisone	100 mg

Source: [Farinde, 2019](#); values in source were multiplied by 2 to equal 20 mg prednisolone dose.

- Antimalarial agents, eg, hydroxychloroquine, chloroquine (3 months)
- Systemic immunosuppressives or disease-modifying antirheumatic drugs, eg, azathioprine, methotrexate, mycophenolate, cyclosporine, tacrolimus (3 months)

Doses of stable permitted therapy (including corticosteroids) may be reduced or discontinued after enrollment because of side effects, abnormal laboratory values, or concurrent illness. No other change to permitted concomitant therapy, with the exception of taper of corticosteroid dose starting at Week 17 (see [Section 5.3.2](#)), is allowed during Study Periods 1 and 2.

In Study Period 3, doses of stable concomitant medication may be decreased based on subject status.

## 7.3 Prohibited Therapies

The following therapies are NOT PERMITTED during the study and require a minimum washout period (in parentheses) before Baseline if discontinued:

- IM, IV, or intra-articular corticosteroids including adrenocorticotropic hormone (1 month)
- IgG (up to 2 months [Note: Subject may enroll before the end of the 2 month washout period if clinical deterioration is experienced after withdrawal of IgG.])
- Plasma exchange or plasmapheresis (3 months)
- Cyclophosphamide or alkylating agents (6 months)
- Other biologic therapies including investigational agents (6 months or 5 half-lives, whichever is longer)
- Rituximab or other B cell depleting therapies (9 months or evidence of persistent B cell depletion after stopping therapy)

Subjects will not be enrolled into the study if they receive any prohibited therapy or any therapy in a prohibited dosage that cannot be discontinued or reduced to a permitted dose before Baseline.

## 7.4 Lifestyle Restrictions

### 7.4.1 Physical Activity

During study participation, there are no restrictions on the subject's normal physical activity, but subjects should not change their physiotherapy regimen from at least 1 month before Baseline to Week 17. After completing Week 17, the subject's physiotherapy regimen can be modified if clinically relevant improvement is achieved; however, any changes should be documented in the subject's eCRF. During Study Period 3, there are no restrictions with regard to physiotherapy.

## 7.4.2 Contraception

Female subjects of childbearing potential or male subjects must use a medically reliable form of contraception for the study duration and for 30 days after the last SC infusion of IMP.

Acceptable methods of contraception are:

- Abstinence where local law permits abstinence as a contraception method and where abstinence is the preferred and usual lifestyle of the subject, including refraining from heterosexual intercourse during the entire period of risk associated with the IMP
- Hormonal methods associated with inhibition of ovulation. Acceptable hormonal methods include: oral contraceptives, contraceptive medication patch, contraceptive medication injection, estrogen/progestin vaginal ring, or contraceptive medication implant
- At least 2 barrier methods. For example, female or male condoms with spermicidal foam or spermicidal jelly, or diaphragm with spermicidal foam or spermicidal jelly. The female condom and male condom should not be used together
- Use of intrauterine device (placed more than 3 months before providing informed consent)
- Bilateral tubal occlusion of female subjects (3 months before providing informed consent)
- Vasectomy of male subjects or male partners/spouses of monogamous female subjects (3 months before providing informed consent)

Periodic abstinence (calendar, symptothermal, postovulation methods), withdrawal (coitus interruptus), spermicides only, and lactational amenorrhea method are **NOT** acceptable definitions of contraception.

## 8 Study Procedures and Visit Schedule

### 8.1 Clinical Procedures

The timing and frequency of the clinical procedures described in the following sections are detailed in the [Schedules of Assessments](#). More frequent assessments may be performed at unscheduled visits if clinically indicated, at the discretion of the investigator. Refer to the provided study manuals for detailed instructions on how and when the scheduled and unscheduled assessments should be performed.

#### 8.1.1 Handling of Study Assessments

During Study Period 1 and Study Period 2, sites should provide at least 2 physicians for study related assessments: a “Treating Physician” and an “Evaluating Physician.” The Treating Physician will be the primary contact for the subject and will be responsible for all safety and

---

treatment-related tasks ([Table 7](#)). It is recommended that the Treating Physician be the Principal Investigator for the study. Tasks assigned to the Treating Physician may be delegated to other qualified site staff according to site general practice. The Evaluating Physician will be responsible for efficacy assessments and the review of all subject-entered data ([Table 7](#)); these tasks may not be delegated. At Baseline before randomization, the Treating and Evaluating Physicians should review and confirm the subject's DM status, to confirm that no clinically relevant improvement has occurred since Screening (see [Section 8.5.3.1](#)), and final eligibility.

In Study Period 3, it is recommended that the Evaluating Physician continues the assessments, if at all possible.

Training for all CSMs and other efficacy assessments will be provided to ensure that the assessments made are attributable to DM and not to other disease. The training will also include detailed instructions on how to complete the assessments. The Treating and Evaluating Physicians should remain the same for each subject through all study visits. Training will be provided to ensure consistency in safety and efficacy assessments in the event that 1 of the physicians is not available for a study visit. The Treating Physician will be notified when the subject has met the criteria for DOW, so that appropriate steps regarding the subject's status per protocol can be implemented. The Treating Physician will have the responsibility to provide the final eCRF signature for each subject.

**Table 7** **Role Responsibilities for Study Assessments**

Treating Physician	Evaluating Physician	Subject

 
• Informed consent
 
• EULAR/ACR criteria
 
• Physician Global Damage Assessment
 
• Eligibility
 
• Medical/Surgical history
 
• DM treatment history
 
• General physical exam
 
• Height and body weight
 
• 12-lead ECG
 
• Vital signs
 
• All laboratory collections
 
• AEs
 
• Concomitant therapies
 
• Physiotherapy documentation
 
• SC infusion training
 
• Randomization/IRT
 
• SC Infusion Diary review
 
• IMP dispensing/accountability
 
• Rescue corticosteroid treatmentB
 
• Withdrawal decision
 
• Safety assessmentsC
 
	
 
• Timed Up and Go
 
• CDASI
 
• MMT-8
 
• MDAATA
 
	
 
• EQ-5D-5L
 
• TSQM-9
 
• WPAI-PH
 
• HAQ
 
• 5-D Itch (Pruritus)
 
• Patient Global Activity
 
• SC Infusion Diary
 

5-D = 5-Dimension; AE = adverse event; CDASI = Cutaneous Dermatomyositis Disease Area and Severity Index; CSMs = Core Set Measures; DM = dermatomyositis; DOW = Definition of Worsening; DVT = deep vein thrombosis; ECG = electrocardiogram; eCOA = Electronic Clinical Outcomes Assessment; EQ-5D-5L = EuroQoL 5-Dimension Questionnaire; EULAR/ACR = European League Against Rheumatism/American College of Rheumatology; HAQ = Health Assessment Questionnaire; IMP = investigational medicinal product; IRT = Interactive response technology; MDAAT = Myositis Disease Activity Assessment Tool; MMT-8 = manual muscle testing of 8 muscle groups; PE = pulmonary embolism; SC = subcutaneous; TEE = thromboembolic event; TIS = Total Improvement Score; TSQM-9 = Abbreviated Treatment Satisfaction Questionnaire for Medication; WPAI-PH = Work Productivity and Activity Impairment Questionnaire for General Health.

A MDAAT includes **Extramuscular Global Assessment** and **Physician Global Disease Activity** components, 2 of the CSMs used for TIS and DOW calculations. The DOW calculation is performed by the eCOA solution and available for Treating Physician assessment of subject's need for rescue corticosteroid treatment.

B Rescue corticosteroid treatment can only be administered if DOW has been met.

C Safety assessments include monitoring for corticosteroid treatment, monitoring for TEEs (including Wells' Criteria for DVT and/or Wells' Criteria for PE), monitoring for hemolysis at Week 2 and Week 5.

## 8.1.2 Demographics and Safety Assessments

Subject demographics and safety assessments to be conducted during this study are provided in Table 8. Clinical laboratory assessments are to be performed at time points as detailed in the [Schedule of Assessments](#). The time windows for each type of assessment are detailed in [Table 14](#).

**Table 8** **Study Procedures: Demographics and Safety Assessments**

Assessment	Description		
Medical/surgical history	
 
Diagnosis and disease status
 
Relevant medical/surgical history, including DM history details
 
DM treatment history
 
Current/concomitant therapies
 
Contraception method (if relevant)
 
		
Demographics	Age, sex, race, and ethnicity (where permitted)		
Physical examination	As per the site's standard procedure, including height and Physician Global Damage Assessment only at Screening		
12-lead ECG	As per the site's standard procedure		
Safety assessments	Refer to Section 8.1.2.1 (Monitoring for Corticosteroid Treatment), Section 8.1.2.2 (Monitoring for Thromboembolic Events), and Section 8.1.2.3 (Monitoring for Hemolysis Risk Assessment)		
Adverse events	Refer to Section 9 (Adverse Events)		
Body weight	As per the site's standard procedure		
Waist circumference	As per the site's standard procedure		
Vital signs	
 
Blood pressure (systolic and diastolic)
 
Respiratory rate
 
Pulse rate (per minute)
 
Body temperature
 
		
Pregnancy test A	Serum test at Screening and urine test at all other assessments for hCG, as indicated for premenopausal females capable of becoming pregnant		
Thrombophilic Abnormality Screen B	
 
Protein C
 
Protein S
 
Lupus anticoagulant
 
Prothrombin G20210A mutation
 
Antithrombin III
 
Cardiolipin antibodies
 
Factor V Leiden mutation
 
		
Hematology	
 
ABO blood group
 
Rh factor
 
Hemoglobin
 
Hematocrit
 
Blood cell counts: erythrocytes, leukocytes with differential counts (neutrophils, basophils, eosinophils, lymphocytes, monocytes), platelets
 
HbA1c
 
		
Muscle enzymes	
 
CK
 
LDH
 
AST
 
ALT
 
Aldolase
 
		
Hemolysis	
 
DAT
 
Indirect bilirubin
 
Peripheral blood smearC
 
Total bilirubin
 
Haptoglobin
 
Direct bilirubin
 
Reticulocytes
 
		
Other biochemistry	
 
Alkaline phosphatase
 
Chloride
 
Glucose
 
Bicarbonate
 
GGT
 
Potassium
 
BUN
 
Sodium
 
Creatinine
 
		

Assessment	Description
Coagulation	• D-dimer
Virus serology	Blood samples are to be tested for HBsAg, HCV antibodies, and HIV-1, HIV-2 antibodies

ABO = blood group type A, type B, type AB, or type O; ALT = alanine aminotransferase; AST = aspartate aminotransferase; BUN = blood urea nitrogen; CK = creatine kinase; DAT = direct antiglobulin test; DM = dermatomyositis; ECG = electrocardiogram; GGT = gamma-glutamyl transferase; HbA1c = glycated hemoglobin; HBsAg = hepatitis B virus surface antigen; hCG = human chorionic gonadotropin; HCV = hepatitis C virus; HIV = human immunodeficiency virus; LDH = lactate dehydrogenase; Rh = Rhesus.

A Serum/urine pregnancy test is to be completed for all females of reproductive potential. A female of reproductive potential is defined as a premenopausal female capable of becoming pregnant. This includes women on oral, injectable, or mechanical contraception and women whose partners have been vasectomized or have received or are utilizing mechanical contraceptive devices.

B Known deficiencies in proteins C, protein S, and antithrombin-III levels and presence of lupus anticoagulant/cardiolipin antibodies (antiphospholipid antibodies) and/or the 2 gene mutations (Prothrombin G20210A and Factor V Leiden) will exclude a subject from the study ([Section 4.1.2](#), Exclusion Criterion 6).

C Peripheral blood smear will only be analyzed for a drop in hemoglobin from the previous study visit  $\geq 1$  g/dL.

Results of laboratory tests should be signed and dated in a timely manner and retained at the study site as source data. Refer to [Section 9](#) for information on how AEs based on laboratory tests should be assessed and reported.

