- Additional laboratory collection for Week 37 is located in [Schedule of Assessments for Rich Pharmacokinetic Sampling](#).
- Optional DNA blood samples for exploratory biomarkers.
- Hematology: hemoglobin, hematocrit, platelets, erythrocytes, leukocytes with differential counts (neutrophils, basophils, eosinophils, lymphocytes, monocytes).
- Muscle enzymes: CK, LDH, AST, ALT, aldolase.

- O. Hemolysis: DAT, total bilirubin, direct bilirubin, indirect bilirubin, haptoglobin, reticulocytes, and peripheral blood smear to check for spherocytosis. Peripheral blood smear will be performed at Week 2 and Week 5 only.
- P. Other biochemistry: sodium, potassium, chloride, bicarbonate, BUN, glucose, GGT, alkaline phosphatase, creatinine.
- Q. Coagulation: D-dimer complex.
- R. MSA and MAA: anti-Jo-1, anti-PL-7, anti-PL-12, anti-EJ, anti-OJ, anti-SRP, anti-Mi-2, anti-p155/140, anti-TIF-1 $\gamma$ , anti-MDA5, anti-NXP-2, anti-PM/Scl, anti-Ro-SSA, anti-Ku, anti-U1 RNP, anti-U3 RNP, anti-HMGCR, anti-SAE-1Ab.
- S. Retention samples at Baseline and Week 53/end of study participation. A virology retention sample should be obtained for all subjects who discontinue at any time during the study.
- T. IMP SC infusions at Week 1 and Week 2 are to be administered only after the visit-specific assessments (except SC infusion diary review) are completed.
- U. Training and supervised IMP SC infusions at the site on Week 1 and Week 2. If additional infusion training at the site is requested by the subject for Week 3 and/or Week 4, no other UNS Visit assessments are required to be performed. Week 3 and Week 4 additional infusion training will be documented in the eCRF. After training is completed, IMP will not be administered during subsequent study visits. For the remainder of their participation in the study, subjects will self-administer IMP at home.
- V. Physiotherapy regimen may be modified starting at Week 17 if clinically relevant improvement is achieved.
- W. Only if subject discontinues IMP treatment before Week 25.
- X. IMP will only be administered at the site for unscheduled visits which occur at Week 3 or Week 4.
- Y. See [Section 5.3.1](#) for DOW criteria and corticosteroid rescue details (Week 9 to Week 25). DOW assessment at UNS Visit only if before Week 25.
- Z.  $\geq 2$  cm improvement from Baseline on 10-cm Physician Global Disease Activity VAS.

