### 8.1.2.3 Monitoring for Hemolysis

For determination of hemolysis, an assessment of clinical signs of hemolysis will be performed at Week 2 and Week 5 and compared to Baseline. In combination with laboratory results confirmed or suspected hemolysis cases will be defined as follows:

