#### ***Suspected hemolysis:***

Subjects fulfilling criterion A and at least 1 of criteria B will be considered to have “suspected hemolysis.”

- Criterion A
  - Drop in hemoglobin of > 1 g/dL since the time of first administration of IMP without clinical evidence of blood loss from gastrointestinal bleeding, menorrhagia, hemoptysis, major hematoma, or injury and not explained by repeated phlebotomy
- Criteria B
  - Presence of minor criteria documented since the time of first administration of IMP, consisting of:
    - DAT positive
    - Haptoglobin < lower limit of normal
    - LDH > ULN
    - Total or indirect (unconjugated) bilirubin > ULN or jaundiced
    - Hemoglobinuria or red/dark urine
    - Hemoglobinemia
    - Spherocytosis
    - Hepatosplenomegaly

If AE of hemolysis is reported, it must be graded by the investigator:

- Grade 1 – Laboratory evidence of hemolysis only (eg, DAT positive, schistocytes, decreased haptoglobin)
- Grade 2 – Clinical evidence of hemolysis and  $\geq 2$  g/dL decrease in hemoglobin
- Grade 3 – Transfusion or medical intervention indicated (eg, steroids)
- Grade 4 – Life-threatening consequences; urgent intervention indicated
- Grade 5 – Death

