### **Week 1**

- Document AEs
- Document concomitant therapies
- Training and supervision of first IMP SC infusion
- Supervision of subject SC Infusion Diary entry

### 8.5.3.2 Week 2

The following procedures will be conducted at 1 week  $\pm$  3 days after the first SC infusion of IMP:

- Body weight
- IMP assignment
- Vital signs
- Safety assessments
- Collection of blood samples to assess the following:
  - Hematology with peripheral blood smear
  - Hemolysis
  - Coagulation
  - Serum IgG
- Training and supervision of IMP SC infusion for Week 2
- Supervision of subject SC Infusion Diary entry
- Document AEs
- Document concomitant therapies
- Document any change to physiotherapy since the previous study visit

Starting with Week 3, the subject will adjust their first dosing day so that no SC infusions occur on the day of a study visit. Site instruction for this transition should be provided.

### 8.5.3.3 Week 5

The following procedures will be conducted at 4 weeks  $\pm$  3 days after the first SC infusion of IMP:

- Body weight
- IMP assignment
- Vital signs
- Safety assessments
- Collection of urine sample for hCG pregnancy test, if applicable

- Collection of blood samples for exploratory biomarkers (serum and RNA analyses)
- Collection of blood samples to assess the following:
  - Hematology with peripheral blood smear
  - Muscle enzymes
  - Hemolysis
  - Coagulation
  - Serum IgG
- Subject SC Infusion Diary review
- Document AEs
- Document concomitant therapies
- Document any change to physiotherapy since the previous study visit
- DOW assessment
- Individual CSMs
- CDASI

#### 8.5.3.4 Week 9

The following procedures will be conducted at 8 weeks  $\pm$  3 days after the first SC infusion of IMP:

- Body weight
- IMP assignment
- Vital signs
- Safety assessments
- Collection of urine sample for hCG pregnancy test, if applicable
- Collection of blood samples for exploratory biomarkers (serum analysis)
- Collection of blood samples to assess the following:
  - Hematology
  - Muscle enzymes
  - Other biochemistry

- Coagulation
- Serum IgG
- Subject SC Infusion Diary review
- Document AEs
- Document concomitant therapies
- Document any change to physiotherapy since the previous study visit
- DOW assessment
- Individual CSMs
- CDASI
- 5-D Itch Score
- Timed Up and Go

### 8.5.3.5 Week 13

The following procedures will be conducted at 12 weeks  $\pm$  3 days after the first infusion of IMP:

- Body weight
- IMP assignment
- Vital signs

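### The condition for reading the blood smear uses a different hemoglobin reference from the hemolysis definition and conflicts with the visit schedule, so at Week 5 spherocytosis may go unassessed in a subject who meets criterion A

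*Protocol*

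**What the plan says.** **When the smear is read.** Protocol Table 8, footnote C: "Peripheral blood smear will only be analyzed for a drop in hemoglobin from the previous study visit" of at least 1 g/dL.

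**What the case definition counts.** Protocol 8.1.2.3, criterion A: "Drop in hemoglobin of > 1 g/dL since the time of first administration of IMP", with no blood-loss or phlebotomy explanation. SAP 11.6.4 repeats it. The same protocol section has the Week 2 and Week 5 assessment "performed at Week 2 and Week 5 and compared to Baseline".

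**When the smear is scheduled.** Note O to Protocol Table 2: "Peripheral blood smear will be performed at Week 2 and Week 5 only". It gives the purpose as a "peripheral blood smear to check for spherocytosis". The Week 2 and Week 5 visit lists (Protocol 8.5.3.2 and 8.5.3.3) both carry the item "Hematology with peripheral blood smear". None of these attaches a hemoglobin condition, and neither does SAP 11.5, which lists the smear among the hemolysis tests.

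**What the smear feeds.** "Spherocytosis" is one of eight minor criteria (criteria B) in Protocol 8.1.2.3. Suspected hemolysis needs criterion A and at least one B. Confirmed hemolysis needs criterion A and at least two B, one of them a positive DAT, and is reported as an adverse event.

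**The concern.** The reading condition and the case definition measure the hemoglobin fall from different starting points. At Week 2 the previous visit is Baseline/Week 1, so the two agree. At Week 5 the previous scheduled visit is Week 2, so they can disagree. A fall spread over both intervals can then satisfy criterion A without ever triggering a reading.

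Criteria B ask for features documented since the first infusion, and spherocytosis on an unread smear is not documented. The definition would then be applied to such a subject with one of its inputs missing. A suspected case could go uncounted, or a confirmed case could be recorded as suspected, which removes the stated route to an adverse event report. SAP 11.6.4 tabulates hemolysis by number and percentage, so the loss would carry into the safety table.

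**Working it through.** The plan gives no figure to reproduce here. The check compares two rules.

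**Inputs**
- d1 = hemoglobin fall from Baseline to Week 2; d2 = fall from Week 2 to Week 5 (g/dL).
- Criterion A at Week 5 (Protocol 8.1.2.3): d1 + d2 > 1.0.
- Smear read under footnote C (Protocol Table 8): at Week 2 if d1 ≥ 1.0; at Week 5 if d2 ≥ 1.0.
- Hemoglobin in 0.1 g/dL steps, each fall from −3.0 to +3.0. This precision is assumed; the documents state none.

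**Week 2.** Criterion A is d1 > 1.0 and the reading condition is d1 ≥ 1.0. Any fall that meets the first meets the second. There is no gap.

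**Week 5.** No smear is read at either visit when d1 < 1.0, d2 < 1.0 and d1 + d2 > 1.0.
- 0.6 + 0.8 = 1.4: criterion A met, neither reading triggered.
- 0.9 + 0.9 = 1.8: the largest such total in 0.1 steps.
- Pairs for totals 1.1, 1.2, …, 1.8: 8 + 7 + 6 + 5 + 4 + 3 + 2 + 1 = 36. The total fall is always below 2.0 g/dL.

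A second group has d1 ≥ 1.0 and d2 < 1.0, for example 1.0 + 0.3. Their smear is read at Week 2 but not at Week 5.

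**Common reference.** If the reading condition were a fall of ≥ 1.0 since the first infusion, criterion A (d1 + d2 > 1.0) would always imply a reading. The enumeration then leaves 0 combinations with criterion A met and the Week 5 smear unread, against 435 under footnote C. These are grid cells, not patients.

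**Straight-line illustration.** Week 2 falls one week after the first infusion and Week 5 four weeks after it, so 75% of a linear fall F occurs after Week 2. The Week 5 smear is unread if 0.75 × F < 1.0, that is F < 1.33. The gap is 1.0 < F < 1.33 g/dL.

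**Unread smears under assumed noise.** The simulation used 400,000 subjects per scenario, independent normal error with within-subject SD 0.3 or 0.5 g/dL, and 25% or 50% of the fall reached by Week 2. All of these are assumptions. Shares are of subjects meeting criterion A at Week 5:

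| True fall by Week 5 | Week 5 smear unread | Unread at both visits |
|---|---|---|
| 1.25 g/dL | 41 to 76% | 23 to 53% |
| 2.0 g/dL | about 11 to 50% | 7 to 16% |

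These are shares of unread smears, not of misclassified cases. The 1.25 g/dL scenario lies inside the straight-line gap and so shows the effect near its largest.

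**When classification changes.** An unread smear matters only if spherocytes are present and either (a) no other criterion B is met, so suspected hemolysis is missed, or (b) a positive DAT is the only other one, so confirmed becomes suspected. Protocol Table 2 schedules DAT, haptoglobin and bilirubin at Baseline, Week 2 and Week 5, and LDH with the muscle enzymes at Week 5, all without a hemoglobin condition.

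**The case against.** The strongest reply is that the smear may not go unread at all. Note O and both visit lists name it unconditionally, and SAP 11.5 adds no condition. If being performed means being read, every smear is read and footnote C is simply out of line. This stands as a real ambiguity. It does not remove the point, because footnote C then contradicts those passages. On either reading the text needs reconciling.

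Second, other criteria cover most of the ground. LDH above the upper limit is itself a criterion B, and LDH is one of the muscle enzymes tracked for disease activity, so some of these subjects will meet criterion B through LDH alone. A positive DAT with raised LDH already makes a confirmed case. This stands, and it is why the effect should be rare.

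Third, the consequences are limited. Suspected cases are also analyzed. Hemoglobin changes that the investigator judges clinically significant are recorded as adverse events whatever the smear shows (Protocol 9.1.1). Discontinuation of study product follows Grade 3 hemolysis, which is not defined by spherocytosis. This also stands.

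A reader might infer from the simulated percentages that a large share of hemolysis cases would be missed. The documents do not support that: the percentages count unread smears under assumed variability, and nothing in the plan says how often spherocytosis would decide a case. A reader might also infer that an unread smear is coded as negative. No passage says so. SAP 11.6.4 has a disregard rule only for hemoglobinuria, hemoglobinemia and hepatosplenomegaly. What follows from the text is only that the feature would not be documented.

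**Conclusion.** The inconsistency holds as written, and it is minor. Footnote C and criterion A use different reference points, and footnote C adds a condition that note O and the visit lists lack. If footnote C governs, falls below 1 g/dL in each interval but above 1 g/dL in total by Week 5 meet criterion A with no smear read. Beyond the wording of the plan, this conclusion assumes only that Week 2 is the previous visit at Week 5. An unscheduled visit with hematology in between would split the fall further and could widen the gap.

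The number of subjects whose classification would change cannot be derived from the documents and should be small. No efficacy result and no thromboembolic stopping rule depends on it.

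**What to change.** Reconcile Table 8 footnote C, criterion A in Protocol 8.1.2.3, note O to Table 2, and the Week 2 and Week 5 visit lists. The condition for reading the two smears should use the same reference point as criterion A, so that every subject who meets criterion A has spherocytosis assessed. The reconciled text should also say whether a smear listed as performed is read in all subjects or only under a condition. The case definition itself need not change.

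The cost is one footnote, one laboratory-manual line and a few more readings of smears that both visits already list.
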